Standard discharge criteria will be applied to all patients, including: Passage of stool, Ability to tolerate solid food and to drink comfortably, Adequate oral analgesia, Patient's willingness to be discharged.

Study Design:

This will be a prospective randomized control trial. Patients who undergo laparoscopic or open colorectal resection, small bowel resection, or ileostomy reversal with small bowel resection that subsequently develop postoperative ileus will be eligible for enrollment.

If they meet inclusion/exclusion criteria, they will be randomized at the time of diagnosis of postoperative ileus to receive Alvimopan as rescue therapy or to receive conservative standard care.

Alvimopan will be prescribed as 1 dose PO with clamping of any NG tube if present for 30 minutes. A subsequent dose (up to a maximum of 3 doses) may be repeated 12 hours later if there has been no recovery of GI function.

Outcome: The primary outcome measure will be hospital length of stay after the diagnosis of POI (date of diagnosis until actual discharge). The secondary outcome measures will be: time to return of bowel function (date and time ileus identified to date and time of passing flatus, stool and tolerating diet), complications (serious adverse events and adverse events of interest 30 days postoperatively), number of re-operations (any reoperations within 30 days of surgery), number of readmissions (any readmissions within 30 days of surgery)

Inclusion Criteria:

1. Subjects who have benign or malignant colonic or rectal disease that have undergone laparoscopic or open colorectal resection, small bowel resection or ileostomy reversal with small bowel resection and subsequently developed postoperative ileus, defined as:
 - a. Patients with symptoms of bloating with or without nausea and vomiting, who require either:
 - i. Return to NPO status after initial diet attempts
 - ii. Undergo placement of a nasogastric tube
 - b. Patients with absence of passage of flatus or stool who are either
 - i. More than 5 days after open surgery without recovery of GI function
 - ii. More than 3 days after laparoscopic surgery or ileostomy closure without recovery of GI function
2. Subjects who are 18 years of age and older
3. Subjects of either gender
4. Subjects who are willing and able to adhere to protocol requirements, agree to participate in the study program and provide written and informed consent.

Exclusion Criteria:

1. Subjects who received Alvimopan preoperatively.

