2. Subjects that have already received scheduled peripherally acting mu-opioid receptor antagonists postoperatively.
3. Subjects that have taken therapeutic doses of opioids for more than 7 days immediately prior to surgery.

4. Subjects with severe hepatic impairment.
5. Subjects with end-stage renal disease.
6. Subjects who are pregnant.
7. Subjects who have undergone imaging suggesting a small bowel obstruction.
7. Subjects with a medical condition that may interfere with the use of the study medication Alvimopan.
8. Subjects who have a condition or general disability or infirmity that in the opinion of the investigator precludes further participation in the study

Data to be collected:

The medical/surgical information below will be collected as part of this research study and is all information already available as part of the patients medical chart.

A) Preoperative variables:

1. Patient name, medical record number
2. Past Medical History
3. Past Surgical history
4. Preoperative Medications (including steroids, anticoagulation, opioid use)
5. Pre-operative Diagnosis
6. Patient Demographics (age, gender, BMI, ASA score)

B) Intraoperative variables:

1. Procedure performed
1. Time of surgery
2. Wound classification
3. Estimated blood loss
4. Intraoperative transfusion
5. Intraoperative IV fluids given
6. Conversion from laparoscopic to open procedure

7. Stoma creation

C) Postoperative variables:

1. Time/day of diagnosis of ileus
2. Abdominal imaging demonstrating ileus if present
3. Time from surgery to medication given
4. Time from ileus diagnosis to medication given
5. Was there return of bowel function (flatus or stool, solid or liquid, stoma output) prior to ileus
6. Intra-abdominal infection/anastomotic leak
7. Time/day of return of bowel function post ileus (flatus and stool- solid or liquid, and stoma function)
8. Time/day of ability to tolerate oral diet (liquid and solid food)
9. Nasogastric tube placement and daily output
10. Duration of nasogastric tube
11. Use and type of anti-emetics given
12. Total number of Alvimopan doses given
13. Post operative complications including reoperation
14. Length of stay in hospital, defined as time from surgery to discharge
15. Length of POI, defined as time from diagnosis of POI until discharge
16. 30-day readmissions

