Study Completion of participation in the study will be 30 days after the date of POI. Any readmission up to 30 days post-operatively to the hospital as a direct result of their surgery will be followed. The patients will follow-up with the surgeon in the office in approximately 3-6 weeks, which is considered standard of care for all patients undergoing colorectal surgery and is not considered part of the research study. Any patient for whom follow-up documentation is missing or incomplete shall be contacted via telephone. The purpose of the call will be to simply determine return to function and outcome. Only a co-investigator shall contact the subject and will identify themselves at the beginning of the call. Any subject can reserve the right not to participate in the phone call interview; they would remain in the study.

Statistical Analysis

Planned Data Analysis:

Descriptive statistics will be computed for all variables including mean \pm standard deviation or median [25th, 75th percentiles] for continuous factors and frequency (percent) for categorical variables.

Univariate analyses will be conducted to compare the distribution of pre-op characteristics across treatment groups using t-test or Wilcoxon rank sum tests for continuous variables and Chi-square or Fisher's exact test for categorical variables.

The hospital length of stay after the diagnosis of POI and time to return of bowel function are defined as the interval between the day of POI diagnosis and day of actual discharge from the hospital, and the day of POI diagnosis and day of return of bowel function. T-test will be used to assess differences in the hospital length of stay after diagnosis of POI or time to return of bowel function across treatment groups. Multivariable linear regression will be conducted to adjust for baseline measurements as well as potential confounding variables such as gender, obesity, and operative time. Backwards variable selection will be used with a removal criteria of alpha > 0.1 . When required, data will be transformed in order to meet normality assumptions.

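### No contact at or after day 30 is planned for every patient, so 30-day complications, reoperations and readmissions treated elsewhere may be missed

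*Combined protocol and SAP*

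**What the plan says.** **Outcomes.** The Outcome paragraph of Study Design lists three secondary outcomes with a 30-day window from surgery: "complications (serious adverse events and adverse events of interest 30 days postoperatively"; "number of re-operations (any reoperations within 30 days of surgery"; and "number of readmissions (any readmissions within 30 days of surgery".

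**Source.** Data to be collected states that the information "is all information already available as part of the patients medical chart". Its list of postoperative variables includes complications with reoperation, and 30-day readmissions.

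**Follow-up.** All of it is in Study Completion:
- "Completion of participation in the study will be 30 days after the date of POI". This starts from a different day than the outcome windows.
- Readmissions up to 30 days after the operation are to be followed, but the sentence is limited to those to the hospital that result directly from the surgery.
- "The patients will follow-up with the surgeon in the office in approximately 3-6 weeks". The plan does not say whether this is counted from surgery or from discharge, and it states that the visit is standard care and not part of the research.
- "Any patient for whom follow-up documentation is missing or incomplete shall be contacted via telephone". What makes documentation incomplete is not defined.
- "The purpose of the call will be to simply determine return to function and outcome". Only a co-investigator may call, and a patient may decline and stay in the study.

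**The concern.** An outcome defined as any event within 30 days needs a source that reaches day 30 for every patient. Here the reach depends on when the clinic books a visit that the study does not control. The one study contact that could close the gap is conditional on an undefined trigger and has no listed questions on events. Nothing in the plan asks about care at another hospital.

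Take a patient who is seen at week 3, has a full visit note, and is admitted elsewhere on day 27. Unless someone judges that record incomplete, no stated step finds the admission.

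What is at stake is the safety side of the trial. The primary outcome rewards earlier discharge, and the Background reports conflicting findings on readmission with alvimopan and names safety as an aim. Readmission is the natural counterweight to a shorter stay, so its count should not depend on clinic scheduling. The Protocol section also says that the patient and surgical team can know the arm, so an undefined trigger leaves room for unequal calling effort between arms.

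**Working it through.** **1. The plan's own figure.** The plan gives no figure for completeness of follow-up. Its only calculated figure is the sample size, used here for the number of patients and the assumed stays. Log-scale SD = √ln(1 + 0.6²) = 0.5545. Then n = 2 × (1.96 + 0.8416)² × 0.5545² / (ln 0.65)² = 26.01, rounded up to 27 per group (two-sided 5%, 80% power; noncentral-t power at 27 is 0.800). With 5% dropout, 27 / 0.95 = 28.4, so 29 per group and 58 in all. This reproduces the plan and is not in dispute.

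**2. Inputs for the gap.**
- Outcome window: 30 days from surgery (Study Design).
- Visit: about day 21 to day 42 from an unstated start (Study Completion).
- Mean stay after ileus diagnosis: 4.25 days control, 2.75 days alvimopan (Sample Size Calculations).
- Day of ileus diagnosis, D: not given; assumed 3 to 6 after surgery.

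**3. Visit counted from surgery.** Gap = 30 − visit day. A week-3 visit leaves 30 − 21 = 9 days (30% of the window), the same in both arms. A day-28 visit leaves 2 days. Visits from day 30 to day 42 leave none.

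**4. Visit counted from discharge.** A week-3 visit falls on day D + stay + 21, so gap = 9 − D − stay, not below zero. Mean stays are used.

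| D | Control gap | Alvimopan gap | Difference |
|---|---|---|---|
| 3 | 1.75 | 3.25 | 1.50 |
| 4 | 0.75 | 2.25 | 1.50 |
| 5 | 0 | 1.25 | 1.25 |
| 6 | 0 | 0.25 | 0.25 |

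**5. Events that could be lost.** The documents give no event rates. Assumed ranges: true 30-day rate 10–20%, share treated elsewhere 10–30%, share of events after the visit 10–40%. Across all 58 patients, per outcome:
- Only late events treated elsewhere are missed: 58 × 0.10 × 0.10 × 0.10 = 0.06, up to 58 × 0.20 × 0.30 × 0.40 = 1.4.
- Every event treated elsewhere is missed, including those before the visit: 58 × 0.10 × 0.10 = 0.6, up to 58 × 0.20 × 0.30 = 3.5.

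**6. What a comparison could show anyway.** With 29 per arm and 10% against 20%, power = Φ[(0.10√29 − 1.96√(2 × 0.15 × 0.85)) / √(0.09 + 0.16)] = Φ(−0.90), about 18%.

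**7. Room for a day-30 contact.** Participation ends on postoperative day 30 + D, that is day 33 to 36 under the assumption. A contact on or after day 30 fits, with D days (3 to 6) to spare.

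**8. The two readmission statements.** Study Design counts any readmission. Study Completion follows those to the hospital that result directly from the operation. The second is narrower on cause and, read literally, on place. The plan does not say which governs the count.

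**The case against.** The best defence is that the chart does most of the work. A late readmission or reoperation at the treating hospital enters its record, nothing ends chart review at the visit, and Study Completion commits to following surgery-related readmissions to day 30. Outside events before the visit can be reported at it. A record ending on day 21 could be judged incomplete for 30-day readmissions and trigger the call, and the word outcome in the call's purpose may be meant to cover the secondary outcomes. All of this stands, and it limits the point to events that may be missed. It does not show that the plan secures the window for every patient, because it relies on readings that the plan leaves open.

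Several stronger readings are tempting and are not supported:
- **That late or outside events will go uncounted.** The chart, the visit and the conditional call will each catch some.
- **That the gap is 12 to 15 days.** That measures from a day-21 visit to the end of participation (day 33 to 36). The three outcomes stop at day 30.
- **That readmission rates would shift by 3 to 7 points.** This is 1/29 to 2/29, and needs one or two missed events all in one arm. The ranges above are for both arms together.
- **That patients who are called are fully covered.** The call has no set date, no listed event questions, and may be declined.
- **That a null readmission result would be made falsely reassuring, or biased by arm.** The Statistical Analysis section names no between-arm test for these outcomes, and power of about 18% makes a null uninformative in any case. A longer gap on alvimopan arises only if the visit is counted from discharge, and is then at most 1.5 days.

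**Conclusion.** The point holds as a gap in how events are found. No contact at or after postoperative day 30 is planned for every patient, the trigger for the call is undefined, and care at other hospitals is not asked about. Events treated elsewhere, above all after an early visit, may be missed.

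The size is modest. The uncovered tail ranges from none to 9 of 30 days; the maximum needs the earliest visit counted from surgery. Counted from discharge it is about 0 to 3 days, on the assumption of ileus at day 3 to 6 and the plan's mean stays. The expected loss is small and rests on rates that the documents do not give. Length of stay, the primary outcome, is unaffected, as is the sample size. This is a cheap improvement to the secondary safety outcomes and does not put the trial's main result in question. The mismatch between the two readmission statements needs settling as well, since extra calls alone would not say which admissions count.

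**What to change.** 1. Make the existing call to every patient in both arms on or after postoperative day 30, unless an office visit on or after that day already documents the full window. This removes the dependence on the undefined trigger and on the visit's start point.
2. Replace the call's stated purpose with fixed questions on readmission at any hospital, reoperation, and serious or of-interest adverse events. Count the answers in the outcomes, and check outside records where they can be obtained.
3. Align the readmission sentence in Study Completion with the definition in Study Design, which counts any readmission.

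The cost is one short amendment and at most 58 brief calls, with no change to sample size or treatment. The calls take co-investigator time, because the plan lets no one else make them. Some patients may decline, so coverage will improve without being complete.

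### The analysis section scores time to return of bowel function in whole days, although the outcome is defined, and its data listed, by date and time

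*Combined protocol and SAP*

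**What the plan says.** The combined protocol and SAP describes this secondary outcome in three places.

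- **Study Design, Outcome paragraph.** It runs from "date and time ileus identified to date and time of passing flatus, stool and tolerating diet". The primary outcome, length of stay after diagnosis, is defined in the same paragraph by date only.
- **Data to be collected, C) Postoperative variables.** Item 1 is "Time/day of diagnosis of ileus". Item 7 is "Time/day of return of bowel function post ileus (flatus and stool- solid or liquid, and stoma function"). Item 8 is "Time/day of ability to tolerate oral diet (liquid and solid food").
- **Statistical Analysis, Planned Data Analysis.** Both length of stay and this outcome are defined as day-to-day intervals, this one between "the day of POI diagnosis and day of return of bowel function". The t-test is applied to each, with the general provision "When required, data will be transformed in order to meet normality assumptions".

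**The concern.** The analysis section does more than mention the outcome loosely. It states a definition, and that definition is coarser than the one in the Outcome paragraph. An analyst who follows it would discard clock times that the data list asks for. The Outcome paragraph uses the date alone for the primary outcome and date plus time for this one, which suggests that the finer scale was intended here.

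What is at stake is precision. Under day-to-day scoring the value depends partly on the hour of diagnosis, so patients can be ranked in the wrong order. Doses are 12 hours apart, so a whole-day scale is also coarser than the treatment schedule.

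A smaller question concerns the end event. The Outcome paragraph lists flatus, stool and tolerating diet. Item 7 covers flatus, stool and stoma function, and item 8 covers diet separately. The documents do not say how these recorded items combine into one time.

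**Working it through.** **1. The plan's own figure.** None is given for this outcome. The only planning figures are for the primary outcome: means of 4.25 and 2.75 days, log-normal, CV 0.6, alpha 0.05, 80% power, 27 per group (Sample Size Calculations). They reproduce with a two-sided test:

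- Log-scale SD = √ln(1 + 0.6²) = 0.5545; log difference = ln(2.75/4.25) = −0.435.
- Noncentral t power is 80.8% at 27 per group and 79.3% at 26.
- 27/0.95 = 28.4, rounded up to 29 per group, 58 in total.

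These inputs are borrowed below as assumptions.

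**2. How day scoring behaves.** With h the hour of diagnosis and T the true interval in hours, the score is floor((h + T)/24).

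- Diagnosis at 23:00, recovery 26 hours later: floor(49/24) = 2 days.
- Diagnosis at 01:00, recovery 46 hours later: floor(47/24) = 1 day.

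The faster recovery receives the longer time.

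**3. Bias.** If diagnosis is equally likely at any hour, an interval with fractional part f rounds up with probability f and down with probability 1 − f, so the expected score equals the true interval. Patients are randomised at diagnosis, so the hour of diagnosis is a baseline quantity and is balanced in expectation. Across simulated control means of 1.5 to 4.25 days and three patterns of diagnosis hour, the mean difference moved by at most 0.02 day.

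**4. Noise.** With diagnosis at any hour, the rounding variance is the average of f(1 − f), which is 1/6 for uniform f (SD 0.41 day). At means of 4.25 and 2.75 days the SDs are 0.6 × 4.25 = 2.55 and 0.6 × 2.75 = 1.65.

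- Standard error, exact times: √((2.55² + 1.65²)/27) = √(9.225/27) = 0.584 day.
- Standard error, whole days: √((9.225 + 2/6)/27) = √(9.558/27) = 0.595 day.

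That is an increase of about 2%.

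**5. Where recovery is likely to lie.** Discharge requires "Passage of stool, Ability to tolerate solid food and to drink comfortably". Recovery that includes tolerated diet should therefore not fall after discharge, so 4.25 days acts as an upper bound on the control mean. The documents do not say how far below it recovery lies.

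**6. Power.** This was simulated with 40,000 trials per scenario, 27 per group and a two-sided t-test at 0.05 on untransformed values. The whole-day ranges cover diagnosis at any hour, 07–17h and 07–11h.

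| Control mean (days) | Alvimopan mean (days) | Exact times | Whole days |
|---|---|---|---|
| 4.25 | 2.75 | 75% | 73%–74% |
| 3 | 1.95 (ratio 0.65) | 74% | 71%–72% |

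**The case against.** **The mismatch is trivial.** This is a secondary outcome with no stated power, and near the 4.25-day bound the loss is 1 to 2 points. That stands, and it is why the point is only a free improvement.

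**The analysis section drops diet from the end event.** A reader might infer this because it names no recovery event and item 7 omits diet. The documents do not support it: the analysis section reuses a term that the Outcome paragraph has already defined with diet included. Item 5 is no evidence either, since it concerns "return of bowel function (flatus or stool, solid or liquid, stoma output) prior to ileus", a different variable. What stands is that the Outcome definition is not fully operational. It could mean one composite or three separate times, it omits stoma function, and it does not say which diet counts.

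**Power falls badly.** At assumed control means of 1.5 to 2 days the same simulation gives 61% to 70% against 74%. The documents give no such means, and they fit poorly with an endpoint that requires tolerated diet, which should fall near discharge.

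**Same-day recoveries score zero and cannot be log-transformed.** This is true, but the plan does not prescribe a log transformation for this outcome, and an offset or another transformation would cope. Such scores should also be uncommon near the bound: with diagnosis at any hour, the simulation puts about 0.2% of control and 1.2% of alvimopan patients at zero.

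**Clock times may not be in the chart.** The combined time/day wording does not guarantee an hour for flatus or diet. The natural reading, given the Outcome paragraph, is that times are recorded, but the fix needs a fallback.

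**Conclusion.** The inconsistency is real and is not resolved elsewhere in the documents. The stated analysis rule is coarser than the outcome's own definition and adds rounding noise that the listed data would avoid. Under the borrowed assumptions the cost is about 1 to 2 points of power at a control mean of 4.25 days and 2 to 3 points at 3 days, and more only if recovery is much faster. These sizes are illustrations, because no mean, CV or effect is given for this outcome.

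A reader might go on to infer a biased treatment comparison or a problem with the primary result. Neither follows: rounding leaves the mean difference almost unchanged, and the primary outcome and sample size do not depend on this definition.

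**What to change.** In Planned Data Analysis, compute time to return of bowel function from the recorded dates and times (hours/24), from item 1 to recovery as defined in the Outcome paragraph. Use the day alone only where no clock time is charted. Use the same wording in the Outcome paragraph, the data list and the analysis section.

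Before analysis, the sponsor should confirm:

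- whether flatus, stool and diet form one last-event composite (for example the later of items 7 and 8) or separate times;
- how stoma function counts;
- whether liquid or solid diet ends the clock.

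The trial is open label, so these choices should be fixed before outcomes are compared by arm. Leave the primary outcome, its day scale, the sample size, the test and item 15 unchanged. The cost is wording only: no new data items and no additional patients.

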For purposes of statistical analysis, a subset analysis may be done based on history of POI, type of operation, BMI, patients' gender, or other clinically significant co-factors. All data will be analyzed with the use of SAS (version 9.4, The SAS Institute, Cary, NC), SPSS statistical software (SPSS Inc., Chicago, IL), or R version 3.6.1 (www.R-project.org). A p-value <0.05 will be considered statistically significant.

Sample Size Calculations:

We conducted the sample size calculation using estimates of length of stay after the diagnosis of POI . We are assuming equal-sized treatment groups and alpha = 0.05.

We assumed that the average length of stay after the diagnosis of POI in no alvimopan group would be 4.25 days, and alvimopan group 2.75 days. Assuming a log-normal distribution, and co-efficient of variation of 0.6 based on prior data, there will be 80% power to detect decreases of at least 35% in length of stay after the diagnosis of POI in the Alvimopan group relative to the control group with 27 patients in each group, a total of 54 patients. Accounting for a dropout rate of about 5%, our enrollment goal will be 58 patients (29 per group).

Reporting of Results

Aggregate and anonymous, in text and table format, for publication in a medical journal.

Consent

A study coordinator will obtain informed consent from participating patients prior to Alvimopan administration. The coordinator will have HIPPA training, certification in human subject protection, and will be familiar with the research protocol. The study coordinator will explain to each participant the purpose of the study as well as give the patient the opportunity to opt out of participation. Consents will be kept in a room accessible only to qualified research personnel working in the CORS department.

Consents will be obtained prior to alvimopan administration. Patients will be offered participation in the study in a private clinic room. Patients will be offered to participate in the study post-operatively at the time of their post operative ileus diagnosis. Alvimopan is not part of the standard of care. It will be administered free of charge without extra financial charges to the enrolled patients.

References:

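### Covariates for the adjusted comparison are chosen by backward elimination from an open list, which lifts its type I error above 5% (slightly with the three named covariates), and no deciding test is named

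*Combined protocol and SAP*

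**What the plan says.** The Planned Data Analysis text sets out two analyses of the primary outcome. The first is unadjusted: "T-test will be used to assess differences in the hospital length of stay after diagnosis of POI". The second is adjusted: "Multivariable linear regression will be conducted to adjust for baseline measurements as well as potential confounding variables such as gender, obesity, and operative time". The next sentence gives the selection rule: "Backwards variable selection will be used with a removal criteria of alpha > 0.1". The same methods serve time to return of bowel function.

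The covariates are introduced as examples, and the baseline measurements are not listed. Nothing says that treatment is exempt from removal. Neither analysis is called primary, confirmatory or supportive, and one threshold covers everything: "A p-value <0.05 will be considered statistically significant".

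The Sample Size Calculations section has no covariate term. It states that "there will be 80% power to detect decreases of at least 35% in length of stay after the diagnosis of POI", comparing two groups without adjustment. Type of operation is absent from the named covariates, although the plan says that "a subset analysis may be done based on history of POI, type of operation, BMI".

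**The concern.** Backward elimination keeps covariates that happen to correlate with length of stay in this sample. The final model then estimates its residual variance, and counts its degrees of freedom, as if those covariates had been fixed beforehand. The residual variance comes out too small, so the treatment p-value does too. The effect grows with the number of candidates, and the plan leaves that number open.

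The missing primary label is a separate problem. Two correlated tests of one hypothesis, each at 0.05, reject a true null more than 5% of the time if a success on either counts, even when both are valid alone. Under the Protocol heading the arm is visible to patient and team in the medical record, so fixing the model and the deciding test in advance is an important safeguard against a choice made after seeing results.

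Leaving out surgical approach may cost precision. It does not bias a randomised comparison.

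**Working it through.** **Inputs from the plan.** On alpha and allocation: "We are assuming equal-sized treatment groups and alpha = 0.05". On mean stay: "in no alvimopan group would be 4.25 days, and alvimopan group 2.75 days". Stay is taken as log-normal with coefficient of variation 0.6, with 27 evaluable patients per group and 58 enrolled after about 5% dropout.

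**Reproducing the sample size.**
- Log-scale SD = √ln(1 + 0.6²) = √ln(1.36) = 0.5545.
- Log-scale effect = ln(2.75/4.25) = −0.435, a 35.3% decrease.
- The normal approximation, two-sided, gives 2 × (1.960 + 0.842)² × 0.5545² / 0.4353² = 25.5, so 26 per group. The noncentral t gives 27 per group with 80.8% power. For a decrease of exactly 35%, t-power at 27 is 79.99%.
- 27/0.95 = 28.4, so 29 per group and 58 in total.

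The plan's figure reproduces as an unadjusted two-sided comparison. Sidedness is not stated, but a one-sided test would need only 21 per group.

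**Type I error.** Null trials were simulated with 54 patients, 27 per group, log-scale SD 0.5545 and no treatment effect. Treatment was held in the model. The candidate with the largest p-value was removed until none exceeded 0.1, and treatment was then tested two-sided at 0.05. The main run used 20,000 trials per cell (Monte Carlo SE √(0.05 × 0.95/20,000) = 0.0015), with two candidates carrying a total R² of 0 or 0.20. A repeat run used 200,000 trials for three covariates (R² 0, 0.1, 0.3) and 60,000 for longer lists (R² 0, 0.2), with up to three prognostic covariates and gender and obesity binary. Pairs below are R² 0 / 0.20.

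| Candidates | Selected model, main run | Selected model, repeat | True SE ÷ reported SE | t-test or fixed model | t-test or selected model |
|---|---|---|---|---|---|
| 3 | 5.53% / 5.32% | 5.5–5.8% | 1.028 / 1.027 | 6.05% / 7.03% | 5.73% / 7.22% |
| 5 | 5.99% / 5.93% | 5.9–6.3% | 1.041 / 1.049 | 6.51% / 7.37% | 6.35% / 7.88% |
| 10 | 6.96% / 6.74% | 6.8–7.4% | 1.086 / 1.085 | 7.02% / 7.38% | 7.51% / 8.51% |
| 15 | 8.03% / 8.42% | 8.1–8.6% | 1.136 / 1.145 | 7.32% / 7.86% | 8.82% / 10.13% |

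The last two columns are from the main run. In the repeat, t-test or selected model reached 8.0% with three candidates (58 patients, R² 0.3) and 10.3% with 15.

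**Comparators.** In the main run the fixed model, with all candidates kept, gave 4.7% to 5.1% and the t-test 4.8% to 5.2%. The repeat gave 4.97% to 5.06% for the fixed three-covariate model.

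**Mechanism and robustness.** With no prognostic covariate, the rule kept on average 0.31 of 3 candidates and 1.96 of 15. With 58 patients and three candidates, error was 5.5% to 5.8%. Without the log transform it was 5.3% to 5.7% with three candidates and 8.9% with 15.

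**How long could the list be?** The Data to be collected section holds about 18 separate preoperative and intraoperative items: medical and surgical history, steroids, anticoagulation, opioids, diagnosis, age, gender, BMI, ASA score, procedure, time of surgery, wound class, blood loss, transfusion, fluids, conversion and stoma. Ten or 15 candidates are therefore possible, but nothing says they would be entered.

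**The case against.** The strongest reply is that the t-test is the main analysis in all but name. It comes first, it is given the task of assessing the difference, and the trial is powered on an unadjusted comparison. It holds its 5% level, so on that reading the selected regression cannot cause a false claim of success.

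The size can also be challenged. With the three named covariates the excess is at most about 0.8 points, and with strongly prognostic covariates (total R² 0.5) a further simulation gave 5.0%. The larger figures need 10 or more candidates, and a data-collection list is not a list of model terms. The either-test figures describe a rule that the plan does not contain. With three non-prognostic candidates, t-test or selected model (5.73%) is even below t-test or fixed model (6.05%), so selection is not what drives that number.

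Most of this stands as a limit on size. The unstated retention of treatment is also minor, since the model exists to estimate its effect. The reply does not supply a sentence naming the primary test or closing the list. Even a supportive estimate would carry a standard error that is too small: the true one is about 3% above the reported one with three candidates and about 14% above with 15.

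**Conclusion.** The concern holds. As written, the selection rule gives an adjusted p-value with type I error above 5%. The excess is slight with the three named covariates, and material (about 7% to 8.6%) if 10 to 15 variables were entered. These figures assume a two-sided test, treatment held in, independent covariates and total R² from 0 to 0.3. They are not bounds, and the inflation fades when covariates are strong enough always to be kept.

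The unnamed deciding test is a second defect. If success could be claimed on either analysis, error would be about 5.7% to 8.0% with three candidates, mainly from testing twice, and 8.8% to 10.3% with 15.

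The t-test and the sample size are sound. The trial's own error rate is at risk only if the selected model, or a choice between the two analyses, decides the result. The plan should be changed to rule that out.

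**What to change.** Delete the backward selection sentence. Specify one linear model for log length of stay with treatment and a short fixed list of covariates known before randomisation and already collected, all kept whatever their p-values. One example is procedure type (open, laparoscopic, ileostomy closure), BMI, gender and operative time, if the recorded time of surgery is its duration. Then name either this model or the unadjusted log-scale t-test as the single primary test, and call the other supportive. The same wording should cover time to return of bowel function.

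The cost is two sentences and no new data. The example list uses 2 + 1 + 1 + 1 = 5 of the 54 − 2 = 52 residual degrees of freedom. Power at the planned effect is 80.8% for the t-test. For the fixed model (10,000 simulated trials per cell) it is:

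| Covariates | R² 0 | R² 0.10 | R² 0.20 |
|---|---|---|---|
| 3 | 78.0% | 82.9% | 86.5% |
| 5 | 76.3% | 80.9% | 84.0% |

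Adjustment therefore loses about three to five points if no covariate is prognostic, and gains about three to six at R² 0.20. If the team doubts that the covariates are prognostic, naming the t-test as primary avoids the loss.
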